4.6 General content

4.6.1 Participant flow

The CONSORT [2] flow diagram for crossover trials will be used to descriptively summarise the course of participants through screening until follow-up throughout the course of the study, this will include the number of:

- Patients fulfilling the inclusion criteria
- Eligible patients
- Patients given/sent a patient information leaflet (PIL)
- Patients approached
- Patients giving consent to participate
- Participants randomised
- Participants allocated to each sequence
- Participants who receive at least one dose of trial drug
- Participants who reach wash-out period
- Participants who reach end of second phase
- Participants who withdraw at any time

Protocol deviations defined in section 3.3.2, and confirmed serious breaches of good clinical practice (GCP) will be summarised descriptively by sequence, including violations of eligibility criteria on entry into the study. The number of withdrawals of consent to the study will be presented, along with reasons for withdrawal. Any notes to file reported for each participant will be presented as a line listing.

4.6.2 Baseline data

Baseline characteristics to be summarised descriptively using means and SDs (or medians and IQRs) or counts and percentages (where appropriate) by sequence and overall will include:

- Patient type (transplant, non-transplant)
- Age (and age group: <11 years, 11-15 years, 16+ years)
- Weight (kg), height (cm) and body surface area (BSA) (m²)
- Resting measurements:
 - O₂ saturations (%)
 - Systolic and diastolic blood pressure (mmHg)
 - Heart rate (bpm)
 - Respiratory rate (breaths per min)
- Heart sounds normal
- Pulses regular
- Signs of heart failure:
 - Respiratory distress
 - Hepatomegaly
 - Pulmonary auscultation findings
 - Ascites
 - Pitting oedema
- History of the following in the last 4 months, and whether related to exercise:
 - Fainting
 - Dizziness
 - Palpitations
 - Chest pain or tightness
 - Unexpected decrease in exercise capacity or fitness level

Baseline medication history, including dose, unit and frequency of drugs received, will be summarised descriptively using counts and percentages by sequence and overall and will include:

- Cardiac drug usage:
 - Amlodipine
 - Aspirin
 - Atorvastatin
 - Bisoprolol
 - Captopril
 - Carvedilol
 - Digoxin
 - Enalapril
 - Furosemide
 - Lisinopril
 - Pravastatin
 - Propanolol
 - Ramipril
 - Spironolactone
- General supportive care drug use:
 - Citalopram
 - Folic acid
 - Forceval
 - Gaviscon
 - Glycozade
 - Lactulose
 - Lansoprazole
 - Movical
 - Multivitamins
 - Omeprazole
 - Panothenate
 - Pizotifen
 - Ranitidine
 - Seravit
 - Sertroline
 - Sytron
 - Thiamine
- Transplant-related drugs:
 - Ciclosporin
 - Mycophenolate mofetil (MMF)
 - Prednisolone
 - Sirolimus
 - Tacrolimus
- Infection prophylaxis drugs:
 - Amoxicillin
 - Azithromycin
 - Cotrimoxazole
 - Granulocyte-colony stimulating factor (G-CSF)
 - Penicillin
- Other drugs

4.6.3 Trial medication data

The dose received by each participant will vary according to the participant's age in the following way:

- Children aged 6-9 years: commence on 100mg once daily for the first month and if well tolerated increase to 100mg twice daily for the remaining 3 months
- Children aged 10-17 years: commence on 200mg once daily for the first month and if well tolerated increase to 200mg twice daily for the remaining 3 months
- Adults aged 18+ years: 200mg twice daily

Dose received by each participant, in each month of each period and in total, will be summarised descriptively using means and SDs (or medians IQRs), along with details of, and reasons for, any dose omissions, by treatment, period and overall.

4.6.4 Other medication data

Any other medications the participant receives during the study will be summarised descriptively using means and SDs (or medians and IQRs) by sequence, treatment, period and overall.

4.6.5 Research blood tests

All research blood tests will be summarised descriptively using means and SDs (or medians and IQRs) or counts and percentages (for eGFR) by treatment and period, with the exception of neutrophil counts, and plasma arginine and cysteine levels, which will be summarised as part of the secondary outcomes. The blood tests to be summarised will be:

- Creatine kinase (U/L)
- Hb (g/L)
- WBC (10⁹/L)
- Platelets
- Lymphocytes
- Monocytes
- Creatinine
- eGFR (mL/min) (<90; >90)
- Urea (mmol/L)
- Sodium (mmol/L)
- Potassium (mmol/L)
- Bicarbonate (mEq/L)
- Calcium (mmol/L)
- Bilirubin
- Alkaline phosphatase (IU/L)
- Alanine aminotransferase (U/L)
- Total protein (g/L)
- Albumin (g/L)
- Brain natriuretic peptide
- Total cholesterol
- High-density lipoprotein (HDL) cholesterol
- Triglycerides

4.6.6 Harms

Harms will be summarised descriptively using concordant and discordant pairs, and line listings for all adverse events (AEs) and serious adverse events (SAEs) where events will be presented

using the safety population according to the treatment the participant received in the relevant period. Line listings of all reported events will include (where appropriate):

- Treatment randomised to in period
- Treatment received in period (if different)
- Date of randomisation
- Date of onset
- Event name
- Expectedness

The additional information will be presented for serious events (where appropriate):

- SAE/SAR/SUSAR full description
- MedDRA system organ class
- SAE/SAR/SUSAR classification (seriousness)
- Relatedness
- Maximum intensity
- Time of onset
- Outcome
- Date of recovery
- Duration of the event
- Unblinding information

Safety blood tests will also be taken in months 1-3, during the wash-out period, and in months 6-8. The results from these tests will be summarised descriptively using means and SDs (or medians and IQRs) by treatment received and overall, and will include:

- Creatinine kinase (U/L)
- Hb (g/L)
- WBC ($10^9/L$)
- Platelets ($10^9/L$)
- Neutrophils ($10^9/L$)
- Creatinine ($\mu\text{mol/L}$) (also collected at week 2 in both periods)
- Urea (mmol/L)
- Sodium (mmol/L)
- Potassium (mmol/L)
- Bicarbonate (mEq/L)
- Calcium (mmol/L)
- Bilirubin ($\mu\text{mol/L}$)
- Alkaline phosphatase (IU/L)
- Total protein (g/L)
- Albumin (g/L)
- Total cholesterol
- LDL
- Triglycerides

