3.3.3 Safety population

The safety population will consist of all randomised participants, included according to the treatment they actually received in each treatment period, and who have received at least one dose of trial treatment.

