3.4 Withdrawals

Participants can withdraw/be withdrawn from treatment and/or follow-up at any stage of the trial at their own discretion or that of the treating clinician. All participants withdrawn from the trial, in addition to those found to be ineligible post-randomisation, will be continued to be followed up until the end of the study, unless they withdraw full consent for further follow-up data to be collected. All data previously collected by the participant will be used in the analysis, unless they have withdrawn full consent from collected data to be used.

4. Statistical analyses and report content

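### AEs and SAEs are aggregated by treatment only through concordant and discordant pairs, which cannot include safety-population participants treated in period 1 alone

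*SAP*

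**What the plan says.** SAP section 4.6.6 names two outputs for clinical events: "Harms will be summarised descriptively using concordant and discordant pairs, and line listings for all adverse events (AEs) and serious adverse events (SAEs". Events are to be presented "using the safety population according to the treatment the participant received in the relevant period".

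Section 3.3.3 defines that population: "The safety population will consist of all randomised participants, included according to the treatment they actually received in each treatment period". A single dose is enough to qualify; completing both periods is not required.

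Three other provisions bear on the point.

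- Section 4.6.6 handles the safety blood tests differently: they "will be summarised descriptively using means and SDs (or medians and IQRs) by treatment received and overall".
- Section 3.4 says that withdrawn participants "will be continued to be followed up until the end of the study", unless they withdraw full consent for follow-up. It also says "All data previously collected by the participant will be used in the analysis", unless consent to that use is withdrawn.
- Section 4.6.1 plans a flow diagram and adds: "The number of withdrawals of consent to the study will be presented, along with reasons for withdrawal".

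Nowhere does the SAP plan a number or percentage of participants with an AE or SAE, or a number of events, by treatment received. It gives no rule for a participant with only one treated period.

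**The concern.** The pairs table is the only place where AEs and SAEs are added up and set against each other by treatment. It cannot be filled for the whole population on which it is said to be based. The participants it leaves out are those treated in period 1 only, and stopping because of an adverse event is one way to become such a participant.

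The SAP's background (section 1.2.1) gives the purpose as learning whether bezafibrate can be given safely as well as effectively, and section 1.2.2 makes the expected benefit conditional on freedom from significant side-effects. With so few participants, losing one or two from the aggregate harms comparison can change what it shows.

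**Working it through.** The SAP gives no figure for harms, so there is none to reproduce. The check sets the definitions side by side and then counts.

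**Step 1: who can form a pair.** For a yes/no event, each participant contributes one cell of a two-by-two table: event on bezafibrate (yes/no) by event on placebo (yes/no). Both entries need exposure to the treatment concerned.

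| Participant | In safety population (3.3.3) | In line listing | In safety bloods by treatment | Forms a bezafibrate/placebo pair |
|---|---|---|---|---|
| Dosed in both periods | Yes | Yes, if an event occurs | Yes, where tested | Yes |
| Stops during period 2, after at least one dose in it | Yes | Yes, if an event occurs | Yes, where tested | Yes |
| Dosed in period 1 only | Yes | Yes, if an event occurs | Yes, where tested | No |

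**Step 2: does continued follow-up restore the pair?** Section 3.4 may supply period 2 observations for someone who has stopped treatment. But section 4.6.6 attributes events to the treatment received in the relevant period, and an untreated period 2 is not exposure to the other treatment. If it is left out, there is no pair. If it is paired, an untreated period stands in for a treated one. The SAP does not say which applies. The counts below take the first option, which follows from the method but is not written down.

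**Step 3: size.**

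Inputs:

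- N = 12 to 15 participants expected (section 2.4).
- k = number of bezafibrate-first participants who have an event in period 1, stop, and take no period 2 treatment. The SAP states no dropout rate, so k = 1 to 3 is an assumption.
- No one else has an event, and all placebo-first participants go on to receive bezafibrate (both assumed).

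Formulas:

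- Pairs available = N − k, of which discordant = 0.
- By treatment received: bezafibrate k/N, placebo 0/(N − k).

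| N | k | Discordant pairs | Bezafibrate, by treatment received | Placebo, by treatment received |
|---|---|---|---|---|
| 12 | 1 | 0 of 11 | 1/12 (8.3%) | 0/11 |
| 12 | 2 | 0 of 10 | 2/12 (16.7%) | 0/10 |
| 12 | 3 | 0 of 9 | 3/12 (25.0%) | 0/9 |
| 15 | 1 | 0 of 14 | 1/15 (6.7%) | 0/14 |
| 15 | 2 | 0 of 13 | 2/15 (13.3%) | 0/13 |
| 15 | 3 | 0 of 12 | 3/15 (20.0%) | 0/12 |

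Each period 1 stopper removes 1/15 = 6.7% to 1/12 = 8.3% of the expected sample from the pairs table.

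**Step 4: direction.** The mirror case, with k placebo-first participants stopping in period 1 after an event on placebo, gives 0 discordant pairs against k/N on placebo and 0/(N − k) on bezafibrate. The pairs table then hides events on placebo. The direction therefore depends on which treatment the stoppers were taking.

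**The case against.** A reader might infer that participants who stop in period 1 vanish from harms reporting, or that the harms summary is biased towards no difference in general. The SAP supports neither reading.

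- The same sentence that plans the pairs also plans listings of all AEs and SAEs on the safety population. A stopper's events are listed with the treatment he was randomised to and, if different, received.
- Safety bloods are summarised by treatment received with no pairing, so pairs are not the only by-treatment summary of harms.
- Someone who stops bezafibrate in period 2 has had both exposures and still forms a pair, and period 1 stoppers on placebo push the other way. Harm on bezafibrate is understated only if harm-related stopping in period 1 falls mainly on that treatment.
- Section 4.6.1 gives the flow of participants, section 4.6.3 gives dose omissions with reasons, and section 4.7 has summaries indicate missing results by sequence. A reader should see that some pairs are missing and, from the sequence, which treatment came first.

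One may add that pairs are a natural summary for a binary outcome in a crossover, that the harms summary is descriptive so no test is distorted, and that with 12 to 15 participants a full listing can be read by eye. Collapsing several events in one participant to yes or no is also offset by listing every event.

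All of this stands, and it limits the point to a gap in the summary rather than a loss of data. It does not close the gap. A listing has no denominator. For non-serious events its fields cover treatment, dates, event name and expectedness; relatedness, intensity and outcome are listed only for serious events, and no listed field marks an event as leading to discontinuation. Counting missing pairs by sequence does not show whether those participants had events.

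**Conclusion.** The point holds in a limited form. Section 4.6.6 states a method for aggregating AEs and SAEs that cannot cover the population fixed in section 3.3.3, and this goes beyond missing detail. Participants treated only in period 1 remain in the listings and the safety blood summaries but leave the only aggregate AE/SAE comparison.

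Where they stopped because of harm on bezafibrate, that comparison understates harm by up to the full difference shown above. This rests on 1 to 3 assumed stoppers, no other events, and untreated periods not being paired. If no one stops in period 1, the pairs table is complete and nothing is lost.

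Severity is minor to moderate: the raw events are reported either way, but the aggregate result a reader would cite could change.

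**What to change.** In section 4.6.6:

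1. Add a table by treatment received giving the number and percentage of participants with at least one AE, the same for at least one SAE, and the number of events. The denominator for each treatment is every participant who took at least one dose of it.
2. Keep the pairs table, restricted to participants exposed to both treatments. State how many incomplete pairs were left out and on which treatment those participants stopped.
3. State that a period followed off treatment does not form half of a pair.
4. Show exposure time by treatment beside the counts.

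The cost is a few lines of SAP text and one table from data already to be collected. There is a small downside: crude percentages by treatment ignore the pairing and may mix unequal exposure times. That is why exposure should be shown and the pairs table kept.

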2.1 Design

This study is a double-blinded, randomised, placebo-controlled crossover study. Treatment will be given in two 4-month long phases and a one month washout period between these where no treatment is given. Participants will be followed up as part of the study for one month after the end of second treatment period (bezafibrate or placebo).

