3.1.2 Exclusion criteria

- Known hypersensitivity to bezafibrate, to any component of the product or to other fibrates
- Known photoallergic or phototoxic reactions to fibrates
- Hepatic dysfunction and/or liver function tests greater than 2x normal
- A shortening fraction of < 25 (or a significant drop in shortening fraction in the previous year)
- Documented atrial or ventricular arrhythmia (atrial/ventricular tachycardia or atrial/ventricular fibrillation) that has not been stabilised with treatment
- Renal impairment (creatinine clearance < 90 mL/min)
- Pre-existing known gallbladder disease
- Recent unspecified significant deterioration in general health
- Prisoners and adults lacking capacity to provide informed consent

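### Safety bloods get only group means or medians, with no participant-level display, no count of abnormal values, and no place for the wash-out sample or the week-2 creatinine

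*SAP*

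**What the plan says.** Section 4.6.6 (Harms) sets the schedule: "Safety blood tests will also be taken in months 1-3, during the wash-out period, and in months 6-8". Creatinine is "also collected at week 2 in both periods". The planned output is one sentence: "The results from these tests will be summarised descriptively using means and SDs (or medians and IQRs) by treatment received and overall". The tests covered include bilirubin, alkaline phosphatase, creatinine and a muscle enzyme printed as "Creatinine kinase (U/L)", presumably the creatine kinase of section 4.6.5.

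The wash-out is defined in section 2.1 as "a one month washout period between these where no treatment is given".

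Other parts of the SAP go further than this:

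- Section 4.6.5 summarises the research bloods with means or medians "or counts and percentages (for eGFR) by treatment and period", so it gives a period split and, for one test, a count either side of 90 mL/min.
- Section 4.5.2 provides line listings for the cardiac MRI data.
- Section 4.6.6 provides line listings for adverse events and serious adverse events, but not for laboratory values.
- The outlier provision in section 4.7 concerns the primary outcomes only.

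**The concern.** Section 1.2.1 makes safe administration part of the purpose of the study, and section 2.4 expects 12 to 15 participants. In a group that small, a liver, muscle or kidney signal is likely to be one or two individuals with abnormal values rather than a shift in everyone. A mean dilutes such a value, and a median largely ignores its height. The summary chosen for the tests labelled as safety tests is therefore not suited to the event those tests are meant to detect.

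Two sets of samples also have no assigned place. The wash-out sample is among the tests being summarised, but no treatment is being received when it is drawn. The week-2 creatinine has no rule for combining it with the monthly values. Both choices would be left to the time of analysis.

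**Working it through.** The SAP states no figure here to reproduce. The check is how far one abnormal value moves each planned statistic.

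**Inputs from the SAP**
- Participants: 12 to 15 expected, 18 at most (section 2.4).
- On-treatment safety samples per participant per period: three (months 1-3 or 6-8), taking one draw per month. Creatinine has four, with week 2 added (section 4.6.6).

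**Assumptions, not from the SAP**
- All on-treatment values for one treatment are pooled over months.
- The abnormal value is 3, 5 or 10 times the usual level (k).
- For SD and quartiles: log-normal values with mean 1 and a coefficient of variation of 30%, 4,000 simulated data sets per setting.

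**Number of values per treatment.** 12 × 3 = 36; for creatinine 12 × 4 = 48.

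**Effect on the mean.** With N values at a usual level of 1 and one of them replaced by k, the mean becomes (N − 1 + k)/N, a rise of (k − 1)/N.

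| Participants | Values N | k = 3 | k = 5 | k = 10 |
|---|---|---|---|---|
| 12 | 36 | 2/36 = 5.6% | 4/36 = 11.1% | 9/36 = 25.0% |
| 12, creatinine | 48 | 2/48 = 4.2% | 4/48 = 8.3% | 9/48 = 18.8% |
| 15 | 45 | 4.4% | 8.9% | 20.0% |
| 15, creatinine | 60 | 3.3% | 6.7% | 15.0% |

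**Effect on the other statistics (12 participants, simulated)**

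| Statistic | No spike | k = 3 | k = 5 | k = 10 |
|---|---|---|---|---|
| Median, N = 36 | 0.96 | 0.97 | 0.97 | 0.97 |
| Upper quartile, N = 36 | 1.16 | 1.18 | 1.18 | 1.18 |
| SD, N = 36 | 0.30 | 0.45 | 0.73 | 1.53 |
| SD, N = 48 | 0.30 | 0.41 | 0.65 | 1.33 |

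The median and upper quartile are the same whether the spike is threefold or tenfold. The SD responds clearly, especially to a large spike, but it does not identify the participant, the visit or the height.

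**If tables were instead made month by month.** With 12 values per treatment per month, the mean would rise by 2/12 = 16.7%, 4/12 = 33.3% or 9/12 = 75.0%. Dilution is smaller, but the participant is still not shown.

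**Counted by participant.** The same event is 1/12 = 8.3% of participants (1/15 = 6.7%, 1/18 = 5.6%), with its full value visible.

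**The case against.** The strongest reply is that the safety assessment does not depend on this one table. Section 4.6.6 also plans concordant and discordant pairs and listings of every adverse event, and section 1.1.2 gives the joint committee regular reports that include safety, with authority to recommend stopping. Creatine kinase, creatinine and alanine aminotransferase are also summarised by period among the research bloods. Whether an abnormal result must be recorded as an adverse event is normally a protocol matter, and its absence from the SAP is no fault. All of this stands. A reader might infer that the safety conclusion rests on the group summary alone; the SAP does not support that.

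Three other stronger readings also fail:

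- *A spike would be hidden outright.* This is close to true for median and IQR only. Under mean and SD, a tenfold value takes the SD from 0.30 to about 1.53, which an attentive reader would notice.
- *Off-drug values are pooled into the bezafibrate group.* Filing each wash-out sample under the preceding treatment, with six participants per sequence, would make 6/(36 + 6) = 14% of bezafibrate values off-drug. But the SAP states no such rule. The sample could enter only the overall summary or stand alone. The fault is that its place is not fixed.
- *The SAP's own entry limits should have been applied.* The criterion "Hepatic dysfunction and/or liver function tests greater than 2x normal" and the creatinine clearance limit of 90 mL/min are exclusion criteria, not on-treatment limits. The safety list also lacks eGFR and the enzyme listed in section 4.6.5 as "Alanine aminotransferase (U/L)".

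Pooling over months is likewise a reading of a sentence that does not mention visits; a month-by-month table would not contradict it. What remains is the lack of any participant-level display, abnormal-value count, period split, or rule for the wash-out and week-2 samples.

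**Conclusion.** The point holds as a weakness in how safety laboratory data will be reported. It biases no treatment estimate or test. For the expected trial size, the planned statistics are poor at showing one participant's abnormal result: a rise in the mean of 5.6% to 25.0% for most tests and 4.2% to 18.8% for creatinine, almost no change in median and quartiles, and an enlarged SD that names no one. These sizes rest on 12 participants with complete samples, values pooled over months, illustrative spikes of 3 to 10 times the usual level and, for the SD and quartiles, an assumed 30% coefficient of variation. The gap itself depends on none of these assumptions, and the SAP already does better for the research bloods and the cardiac MRI data.

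**What to change.** Amend section 4.6.6 before the data are analysed. For each safety test, by treatment received and period, add:

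- each participant's worst on-treatment value, with the adverse direction (high, low or both) stated per test;
- the number of participants with any on-treatment value outside the laboratory reference range, or outside limits that the clinical team states in advance;
- individual profiles over time, showing period and treatment.

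Show the wash-out sample in its own column and exclude it from both treatment summaries. Show week-2 creatinine as its own visit. The planned means and medians can stay alongside.

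The cost is a few sentences in the SAP and some extra table rows and plots from data already being collected. The downside is slightly longer safety output. The adverse event listings and committee review continue unchanged as additional safeguards.
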